3.2.2 Potential Benefits

Nocturnal enuresis is a source of depression, social isolation, and has even been linked to teenage suicide, and physical abuse of children. It is also significant financial and emotional drain on parents and families. Current enuresis alarm treatments are marginally effective requiring parents to seek specialist medical advice, which may not be readily available, and to spend large amounts of money on drug therapy and diapers. Many parents have an aversion to giving their children medications such as DDAVP or Imipramine to manage their enuresis

because of potential side effects, even though rare. A mechanism that allows for early warning of an impending urination event to the patient and parent is a boon for society and to the patients' own self-esteem and the families economic well-being. Our non-invasive, home-based, predictive alarming system will help satisfy these treatment needs by providing a superior conditional enuresis alarm therapy while keeping the child dry at a fraction of the cost of drug therapy or diapers with virtually no negative side-effect risk.

4 Study Objectives

4.1 Hypothesis

Our hypothesis is that the GoGoband® is more effective than SNEA and Desmopressin in the treatment of Nocturnal Enuresis

4.2 Primary Objective

The primary objective of this study is to determine whether the GoGoband®] is as effective or more effective in comparison to children who use SNEA in a population of MNE patients with no underlying ADHD in a 3 month period.

4.3 Secondary Objectives (if applicable)

To ascertain if familial incidence of nocturnal enuresis has an effect on outcomes

5 Study Design

5.1 General Design Description

We propose the following study in patients who have been evaluated for primary nocturnal enuresis in our Yale New Haven Clinics.

- All patients to be evaluated for nocturnal enuresis will undergo standard evaluation and initial treatment for nocturnal enuresis which includes:
 - Assessment Of Bowel Habits,
 - Fill Out A Questionnaire To Evaluate For Voiding Dysfunction
 - Treatment with routine bedwetting protocol of:
 1. Stopping drinks 1 HR before bedtime, meals at least 3 hrs before bedtime, eliminating milk and ice cream from dinner and on, making sure that bowel movements are occurring 4 times per week and treating appropriately if necessary.
 2. On return visit bedwetters and parents will be given the option of using medication , no further treatment, or alarm therapy.
 3. If patients choose alarm therapy, they will be asked if they wish to participate in the Randomized study comparing GoGoband® vs SNEA.
 4. Alarms will be provided to the patients free of cost to participants
 5. Patients in the alarm group will be treated for 3 months continuously.
 6. Patients in the SNEA group will record nightly if they wet their clothes and the report will be recorded and reviewed weekly
 7. GoGoband® patients' data will be automatically saved on the HIPPA Compliant servers and subsequently reviewed at the end of the week.

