3.2 Assessments

3.2.1 Efficacy

SNEA: Device Will be provided to the patient

1. A log will be kept document that the patient wore the device that night
2. Mark if they were wet or dry that morning
3. if the alarm sounded that night
4. whether the device was on the patient in the morning
5. A log will be kept if the patient took ibuprofen or any Ansaïd that day

GoGoband®: Device Will be provided to the patient

1. A log will be kept identifying that the patient wore the device that night
2. Mark if they were wet or dry that morning
3. if the alarm sounded that night
4. whether the device was on the patient in the morning
5. A log will be kept if the patient took ibuprofen or any ansaid that day

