3.2.5 Biomarkers (if applicable)

3.3 Study Procedures

3.3.1 Study Schedule

Total study time is 3 months exclusive of prestudy visit which should be within 2 months of start of study.

Prestudy entry:

- all Nocturnal enuresis patients are all evaluated with physical examination and post void residual check.
- DVQ questionnaire is administered
- Inclusion and exclusion criteria evaluated
- treated with standard urotherapy previously described.

Visit 1:

- Confirm that patient has no daytime voiding symptoms identifying patient has MNE and qualifies for study
- Offer the patient treatment Choices:

2000031281

February 20, 2024

- medical treatment if so no longer candidate for study
- Alarm therapy: If Alarm therapy is chosen: randomize into SNEA or GoGoband®
- Consent to be signed
- Dispense alarm that day or have patient return within a week to have the alarm demonstrated and how to setup and to take home.
- Subject log is given along with alarm.

Visit 2:

- 1 month virtual or in person to follow progress,
- log is handed in, scanned into my chart, faxed or emailed
- new log dispensed

Visit 3:

- 2 month virtual or in person to follow progress
- log is handed in, scanned into my chart, faxed or emailed
- a new log dispensed

Visit 4:

- 3 months virtual or in person to close out study,
- log is handed in, scanned into my chart, faxed or emailed.
- Patients are informed that they can keep the alarm and continue to use it if they wish.

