4.6 Data Quality Assurance

Data quality consists of data logs which need to be maintained by the patients. Other than reminding patients that the data needs to be entered we are constrained by lack of being able to record events if the patient does not. The GoGoband® system has a built in system of recording wet dry events therefore this data will be available consistently as long as the patients use the device.

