4.8 Access to Source

Source documents such as the log forms will be entered by the principal investigator [name], PhD into a dedicated spreadsheet which will be deidentified and maintained on a Yale University protected box drive. Once data is entered the documents will be scanned and entered to Epic as media files as per routine protocol for the department of urology.

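### The plan does not say which record decides a wet or dry night in the GoGoband arm, or what counts as wet, and Section 5.1 describes capture that differs by arm

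*Combined protocol and SAP*

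**What the plan says.** The combined protocol and SAP describes the recording of wet and dry nights in several places.

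- **Section 5.1, SNEA arm:** "Patients in the SNEA group will record nightly if they wet their clothes and the report will be recorded and reviewed weekly".
- **Section 5.1, GoGoband arm:** "data will be automatically saved on the HIPPA Compliant servers and subsequently reviewed at the end of the week".
- **Section 3.2.1 (Efficacy), both arms:** the same five-item log is listed under each device, including "Mark if they were wet or dry that morning". The GoGoband list opens with "A log will be kept identifying that the patient wore the device that night". Both lists also ask whether the alarm sounded.
- **Section 3.3.1:** "Subject log is given along with alarm", with logs collected at visits 2 to 4 and no restriction by arm.
- **Section 4.6:** data quality rests on the patients' logs, which cannot be completed for a family that does not record. The section then adds that GoGoband has its own wet/dry recording and that "this data will be available consistently as long as the patients use the device".
- **Section 4.8:** "Source documents such as the log forms will be entered by the principal investigator" into the study spreadsheet.

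Sections 5.2.1 and 3.4.3.1 list the outcome only as a wetting event, dry or wet. They name no source and no definition.

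**The concern.** The primary objective is a comparison of dry-night rates, and the cured and partial-response categories are built from the same nights. Families know which device they have. If SNEA nights come from a family record and GoGoband nights from a device record, the method of measurement is tied to treatment, and randomisation does not remove the resulting error.

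The two sources could differ in at least two ways:

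- **Unworn nights.** The device record covers only nights of use. A night without the device would drop out of the GoGoband data, while an SNEA family could still log it. If children wet more on such nights, this favours GoGoband.
- **Wetting that was changed.** A child woken by the alarm after a small leak and changed could be marked dry in the morning, whereas a moisture record would count the event. If this happens in the SNEA log but not in the server data, it favours SNEA.

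With no governing source named, the choice could also be made after both records have been seen.

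**Working it through.** **1. The plan's own figure.** Section 3.4.2 gives 29 participants, from proportions 0.5 and 0.8, one-sided 5% error, 80% power and ratio 1. The unpooled formula gives

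n = [0.5×0.5 + 0.8×0.2] × [(1.645 + 0.842)/0.30]² = 28.16, rounded up to 29 per arm.

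The figure reproduces. It does not depend on the recording instrument, and a common instrument would not change it.

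**2. The sections side by side.**

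| Question | 5.1 | 3.2.1 Efficacy | 4.6 |
|---|---|---|---|
| SNEA source | family record | family log | family log |
| GoGoband source | server | family log | family log, plus device record |
| What is recorded | wet clothes (SNEA); not stated (GoGoband) | wet or dry in the morning | wet/dry events (device) |
| Unworn nights, GoGoband | not addressed | wear and wet/dry are separate items, so they can be logged | absent from the device record |

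No section says which GoGoband source prevails, or what happens when log and device disagree.

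**3. Illustrative sizes.** The documents give no error rates or wear rates. Every rate below is an assumption unless a source is given.

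*Unworn nights.* Assume 80% dry on worn nights and 20% of nights unworn.

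- If unworn nights are also 80% dry, the overstatement is 0.
- If they revert to the purchaser cohort's baseline in Section 2.1.2 (6.2 wet nights a week, so 0.8/7 = 11.4% dry), the all-night rate is 0.8×0.80 + 0.2×0.114 = 0.663. The overstatement is 13.7 points.
- If they revert to the entry minimum in Section 5.3 (2 wet nights a week, so 5/7 = 71.4% dry), the rate is 0.8×0.80 + 0.2×0.714 = 0.783. The overstatement is about 2 points.

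*Changed nights marked dry.* If 10% or 20% of SNEA wet nights were logged dry, a true 50% would read 0.50 + 0.10×0.50 = 55% or 0.50 + 0.20×0.50 = 60%.

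*The 29/30 rule.* With independent nights and dry probability q, P(cured) = q³⁰ + 30(1−q)q²⁹.

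| True dry rate | Error in one arm | Observed q | P(cured), true | P(cured), observed |
|---|---|---|---|---|
| 0.90 | 5% of wet nights missed | 0.905 | 18.4% | 20.8% |
| 0.90 | 20% of wet nights missed | 0.920 | 18.4% | 29.6% |
| 0.95 | 10% of wet nights missed | 0.955 | 55.4% | 60.6% |
| 0.95 | 1% of dry nights called wet | 0.9405 | 55.4% | 46.0% |
| 0.95 | 2% of dry nights called wet | 0.931 | 55.4% | 37.7% |

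Missing 5% to 20% of wet nights at a true 0.90 moves the night-level rate by only 0.5 to 2 points, but moves the cured proportion by about 2 to 11 points.

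*Effect on the test.* Take 50 per arm (Section 5.3.1), a one-sided 5% test and the normal approximation with pooled null variance. If true patient-level success is 0.5 in both arms, a shift of 2, 5 or 10 points in favour of GoGoband raises the rejection probability to about 7%, 13% or 26%. If the true proportions are 0.5 and 0.8, a shift of 5 or 10 points against GoGoband lowers power from 94% to 83% or 66%.

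**The case against.** The strongest reply is that a common instrument already exists. Section 3.2.1 (Efficacy) sets the same log for both arms, Section 3.3.1 hands it out with either alarm, and Section 4.8 makes log forms the source for the spreadsheet. On that reading the server data are only a supplement. This stands as far as it goes, and it makes the defect an unresolved choice of source.

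A reader might infer more: that the arms are measured by different instruments under three definitions of wet, so that part of any difference is an artefact. The documents do not support that.

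- The artefact arises only if mixed sources are analysed, and no section says they will be.
- Wet clothes, wet or dry in the morning, and device wet/dry events are three descriptions, none of them an operational definition. The alarm log form (Appendix 2) is listed but is not in the supplied text.
- That the moisture sensor feeds the server record is a reasonable inference, not a statement.
- The log also asks whether the alarm sounded. By the classification text in Section 6.1.1 a standard alarm sounds on a small quantity of urine, so an SNEA leak that was changed would often leave a trace.
- The 13.7-point figure uses a baseline from device purchasers and full reversion on unworn nights. At the entry minimum it is about 2 points.
- Night-level shifts should not be set against the 30-point planning difference. Section 3.4.2 sizes the trial on participants and does not call its proportions dry-night rates.
- The problem is not beyond repair. If logs are kept in both arms, they can be analysed on their own.

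The last point holds only as far as the GoGoband logs are completed. Section 4.6, which presents the device record as the consistently available source, gives little assurance that they will be the record used.

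**Conclusion.** The concern holds as an unresolved source and an undefined outcome, and should be fixed. Sections 5.1 and 4.6 describe capture that differs by arm, Section 3.2.1 (Efficacy) describes a common log, and nothing decides between them for a GoGoband night. If Section 5.1 is followed, ascertainment is confounded with treatment and the dry-night, cured and partial-response comparisons may be biased in either direction. If the common log is analysed, this particular bias is absent, although unmasked self-report remains in both arms.

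Neither sign nor size can be derived from the documents. The illustrations rest on assumed error and wear rates and, for the cure rule, on independent nights. They show only that small arm-specific errors, nearly invisible in the night-level rate, can matter at the 29/30 threshold.

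**What to change.** Reconcile Sections 5.1, 3.2.1 (Efficacy), 3.4.3.1 and 4.6 so that they state the following:

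1. The efficacy outcome in both arms comes from the identical nightly family log, completed every night whether or not the device was worn.
2. A night is wet if there is any wetting of clothes or bed between bedtime and rising, including wetting that triggered an alarm and was changed.
3. GoGoband server data are used only for device mode, wear time and a within-arm agreement or sensitivity analysis.

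**Cost.** The log is already planned in both arms, so the change is protocol wording and, if the form does not already carry this definition, a reworded log item. The GoGoband arm gives up the automatic record as its primary source and accepts the missingness of a family log. Self-report by families who know their device remains in both arms. Log entry by someone masked to arm would be a worthwhile but separate step and is not needed here.

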5.1.1 Study Date Range and Duration

Each patient will be in the study for 90 days. The study duration will be 2 years to accrue enough patients willing to participate in the study and 1 year for data analysis and publication

5.2 Outcome Variables

5.2.1 Primary Outcome Variables

Variables:

Wetting event: Dry or Wet

Did patient wear the device: yes or no used to measure compliance

Did patient take the medication: yes or no used to measure compliance

Is the patient considered cured (dry 29/30 nights) : yes or no

Is the patient partially better (improvement of 50% or more compared to pre treatment)

Does the patient show no improvement (<50% improvement compared to Pre treatment)

5.2.2 Secondary and Exploratory Outcome Variables (if applicable)

Did parents wake to assist child when alarm goes off: yes or no (2 nd measure of compliance)

What is the role of parental assistance in Dry night rates.

Evaluate parental nocturnal enuresis rates as children and cessation of enuresis and compare to final success outcomes of participants.

5.3 Study Population

1. Any patient seen in clinic for nocturnal enuresis in our clinic is eligible as long as they wet the bed a minimum of 2 times per week and are over 6 years and under 21 years of age
2. All patients will have filled out a DVQ and found not to have daytime voiding issues
3. All patients will not have evidence of hyperactivity or learning difficulties as measured by the DVQ
4. All patients will have a post void residual test prior to randomization. If residual is greater than 30 cc they will be excluded from participation based on the possibility of dysfunctional voiding problem.

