2.1.1 Device Preclinical Experience

GoGoband® is a new biometric, artificial intelligence and machine learning powered wearable bedwetting alarm that uses Pavlovian or classical conditional training to increase the effectiveness of enuresis alarm treatment. This is accomplished with the use of heart rate data, heart rate variability (HRV) analysis and real time monitoring that combines the use of algorithms developed with machine learning to learn the individual profile of each patient. Each device consists of a photoplethysmography (PPG) heart rate sensor worn on the calf, a bedside tablet, a Bluetooth moisture sensor and a parent app. The first 7-10 wetting episodes are utilized to develop the individualized program based on HRV data to predict when an impending urination event is going to happen. Artificial intelligence in our web-based database develops hundreds of thousands of models and selects the best one to predict a urination event. As time moves along the machine learning continues to modify the signaling parameters as the child's bedwetting improves. In the weaning phase the system gradually eliminates alarming episodes in a controlled fashion and as the children continues to progress it will eliminate all alarming. Once this stage is completed and the child remains dry for a week consecutively, they are deemed cured. This process can last a few days to several months with some children using the alarm remaining dry on day one and never having another accident without the alarm going off and others remain in need of the system to continue to wake them and keep them dry.

Our most recent data indicates that we can achieve a dry night rate as high as 94% in compliant patients that use the device at least 80% of the time. these results are in stark contrast to the best reported outcomes of 70% in European SNEA studies.

In summary the GoGoband® is a new biometric, artificial intelligence and machine learning powered wearable bedwetting alarm that uses Pavlovian or classical conditional training to increase the effectiveness of enuresis alarm treatment. The non-intelligent alarms on the market today rely on a form of operant conditioning which in many cases relies on negative reinforcement i.e. waking the child up to change the bed or do their laundry.

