BACKGROUND: Bedwetting alarms (BWA) have been around for more than half a century with little innovation in the field. GOGOBand® utilizes real time heart rate variability (HRV) analysis and applied artificial intelligence (AI) to create an alarm that is capable of waking the patient prior to wetting. Our Aim was to evaluate the efficacy continues to remain high with the addition of 20 new patients to our servers. **METHODS:** Data was retrieved and analyzed from our servers, of patients who purchased the GOGOBand® which includes a heart rate monitor, moisture sensor, bedside tablet and app for the parents phone in this study. There are 3 modes, training, where the individualized HRV parameters are used to build the alerting model. Once patients are done with training, they enter the Predictive mode where they receive an alarm if an impending urination event is noted. In Weaning mode the alerting is gradually suppressed. Only patients that used the alarm for more than 30 days were included. Data analysis was done with SPSS and xlstat. **RESULTS:** A total of 60 subjects that have used the system for more than 30 nights were included in this analysis. Gender mix was 46 males (76.6%) and 14 females (23.3%). The mean age of the subjects is 10.2 yrs. Subjects wet the bed an average of 6.2 nights per week prior to treatment. Severity and number of accidents per night had no impact on the ability to achieve dryness with the GOGO Band® device in logistical regression analysis. The data was also segregated based on compliance since it became clear during the analysis that compliant patients achieved better results than non-compliant patients. A crosstab analysis was performed and is reported in table 1. The data clearly indicates that compliant patients >80% are able to remain dry 96% of the time once they enter the weaning phase. **CONCLUSIONS:** Our findings indicate a 96% success rate in patients that are weaning, this translates to 1.2 wet nights per 30 days. This compares to the same group when starting the use of the alarm had only 14.4 dry nights per 30 days. The addition of the 20 patients indicates that that our results are enduring and seem to be improving as we continue to increase the number of patients that are on the system.

compliance groups		training	predictive	Wean	Total	
<=65%	dry	Count	311 _a	881 _b	1584 _c	2776
		% within group	59.70%	77.30%	87.50%	80.00%
	wet	Count	210 _a	258 _b	226 _c	694
	% within group	40.30%	22.70%	12.50%	20.00%	

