3.4.3 Planned Analysis

3.4.3.1 Primary Analyses

Outcomes will be evaluated between the 2 groups using crosstab analysis of the data for the following data :

Wetting event: Dry or Wet

Did patient wear the device: yes or no used to measure compliance

Did patient take the medication: yes or no used to measure compliance
 Is the patient considered cured (dry 29/30 nights) : yes or no
 Is the patient partially better (improvement of 50% or more compared to pretreatment)
 Does the patient show no improvement (<50% improvement compared to Pretreatment)
 Logistic regression analysis may be performed on the incremental wet dry data vs time to achieving dryness

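### The dry-night and cure comparisons ignore how often each child wet the bed at entry, which costs precision, and no wet-night count after urotherapy is named

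*Combined protocol and SAP*

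**What the plan says.** **Entry.** Under 5.3 a child is "eligible as long as they wet the bed a minimum of 2 times per week". There is no upper limit, and the period over which the count is taken is not given.

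**Timing.** For the prestudy visit, 3.3.1 lists "Inclusion and exclusion criteria evaluated" and, after it, "treated with standard urotherapy previously described". It also states: "Total study time is 3 months exclusive of prestudy visit which should be within 2 months of start of study". Section 3.3.3 likewise puts screening at the initial visit, and 5.1 offers alarm therapy only at the return visit, once the routine measures have been tried. At Visit 1 the one named check is "Confirm that patient has no daytime voiding symptoms identifying patient has MNE and qualifies for study". The nightly log is first handed out with the alarm at that visit.

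**Allocation.** The randomization text under 6.1.2 provides 100 envelopes, 50 per device. Age is the only variable that it, or the interim analysis in 3.4.3.5, tries to balance.

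**Analysis.** Section 3.4.3.1 says: "Outcomes will be evaluated between the 2 groups using crosstab analysis of the data". The items listed include wet or dry nights, cure (29 dry nights of 30), and improvement above or below 50% from pretreatment. The improvement items use pretreatment frequency. Wet/dry nights and cure do not. A logistic regression on the wet/dry data is optional and names no baseline term. Section 3.4.4, Subsets and Covariates, is a heading without text.

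**Device and pilot.** Section 2.1.1 says: "The first 7-10 wetting episodes are utilized to develop the individualized program based on HRV data". Both abstracts in 2.1.2 report: "Subjects wet the bed an average of 6.2 nights per week prior to treatment". The next sentence in each reports that neither severity nor the number of accidents per night affected whether dryness was achieved.

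**The concern.** The Synopsis objective is the dry-night rate on each device. A child who wets twice a week is already dry on most nights before any alarm is fitted; a child who wets nightly is never dry. A baseline variable with that range is a natural candidate to predict both dry nights and cure. The trial has to ask about it anyway, for eligibility and for the 50%-improvement outcomes, yet leaves it out of the two comparisons where it could reduce noise.

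At stake are a wider confidence interval than necessary, and a chance difference in entry frequency between arms that the planned tables cannot separate from a device effect.

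Timing adds a smaller problem. If the count precedes urotherapy by up to 2 months, it may no longer describe the child at randomization. A child whose wetting has since fallen below the 5.3 floor could still be enrolled, because no step tells the clinic to count again. Low-frequency children also take longer to supply the wetting episodes from which the GoGoband builds its model.

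**Working it through.** **1. The plan's own figure.** Section 3.4.2 uses 0.5 against 0.8, one-sided 5%, power 0.8, ratio 1. The unpooled formula gives n = (p1q1 + p2q2)(z0.95 + z0.80)² / d² = (0.25 + 0.16)(1.645 + 0.842)² / 0.30² = 28.2, so 29 per arm. The stated 29 reproduces as a per-arm number. The planned difference of 30 points gives a scale for what follows.

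**2. Untreated dry rate.** For w wet nights a week it is 1 − w/7, taking each of the weekly times in 5.3 as one night.
- w = 7: 0%
- w = 6.2 (pilot mean): 11.4%
- w = 2 (floor): 71.4%

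**3. Chance imbalance between arms.** The documents give no SD for entry frequency. I assume 1.2 to 1.7 nights a week; the upper end is about what an even spread over 2 to 7 would give. The number per arm is 50, from 5.3.1 and the envelope count (the Synopsis gives 150 in total). The standard error of the difference in mean untreated dry rate is (SD/7) × √(2/50) = (SD/7) × 0.2.

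| Assumed SD (nights/week) | SD of untreated dry rate | SE of difference | 95% range |
|---|---|---|---|
| 1.2 | 17.1 points | 3.4 points | ±6.7 points |
| 1.7 | 24.3 points | 4.9 points | ±9.5 points |

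That is about ±7 to ±10 points in the baseline, not in the result.

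**4. How much reaches the outcome.** The carried part is the imbalance times the slope of on-treatment dry rate on untreated dry rate. If the two have equal SDs, the slope equals their correlation r. With r assumed to be 0.3 to 0.5, the carried range is 0.3 × 6.7 = 2.0 to 0.5 × 9.5 = 4.8, or about ±2 to ±5 points.

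**5. Gain from adjustment.** For a linear covariate the variance of the comparison falls by about r²: 0.3² = 9% and 0.5² = 25%.

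**6. Training time.** Nights needed = episodes / (w/7), as a share of the 90 days in 5.1.1. This assumes one episode per wet night, nightly use and no improvement during training.

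| Wet nights/week | 7 episodes | 10 episodes |
|---|---|---|
| 2 | 24.5 nights (27%) | 35 nights (39%) |
| 3 | 16.3 nights (18%) | 23.3 nights (26%) |
| 6.2 | 7.9 nights (9%) | 11.3 nights (13%) |

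**The case against.** **Randomization already deals with this.** Chance imbalance is not bias, and a correct standard error for the unadjusted comparison allows for it. This stands. Adjustment buys precision; it does not rescue an invalid analysis.

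**The pilot found that severity did not matter.** This is the only evidence in the documents on whether entry frequency predicts outcome, and it points against the correlations assumed above. It comes from 40 and then 60 uncontrolled purchasers with more than 30 days of use, averaging 6.2 wet nights a week, and it concerns achieving dryness rather than the nightly rate. It says little about children near the floor. It does leave the gain uncertain.

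**The comparison does use pretreatment frequency.** That is true of the two 50%-improvement outcomes, so a reader should not infer that baseline is ignored throughout. The gap is confined to dry nights and cure.

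**The count may not precede urotherapy.** No sentence dates it. The order rests on the list in 3.3.1, on screening at the initial visit in 3.3.3 and on the return-visit step in 5.1. Visit 1 also speaks of qualifying for the study, which could be read as a full re-check, although it ties this to daytime symptoms. Under 5.1 a nearly dry child may also choose no further treatment. The order is the natural reading, but an inference.

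**Training nights belong to the device.** Section 3.1 seeks dry-night rates for the two devices, so counting those nights is a fair whole-device comparison. That stands. The abstracts also mention accidents per night; more than one in a night could shorten training.

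**Conclusion.** The point holds as a loss of precision. Entry frequency can vary from 2 to 7 wet nights a week, and neither allocation nor the dry-night and cure comparisons take account of it. Under the assumed SDs, baseline imbalance has a 95% range of about ±7 to ±10 points with 50 per arm. Perhaps ±2 to ±5 points of this would carry into the result, against a planned 30. Adjustment would cut variance by 9% to 25% if r is 0.3 to 0.5. The SDs, the correlations and the equal-SD step are assumptions, and the pilot leaves the gain in doubt.

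Four stronger readings are tempting, and the documents do not support them.

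- *The trial's result would largely reflect entry frequency.* That can describe the level in each arm, but not the randomized difference.
- *Low-frequency children would spend a third or more of the study in training.* At the floor the range is 27% to 39%. It passes a third only with 9 or 10 episodes (31.5 nights, 35%, at 9; 28 nights, 31%, at 8), and at 3 a week it never does. Larger shares need a fall below the floor after urotherapy, which nothing in the documents reports.
- *A child near the floor could count as cured with little help from the alarm.* At 2 a week with independent nights, the untreated chance of at most 1 wet night in a fixed 30 is (5/7)^30 + 30(2/7)(5/7)^29 = 0.05%.
- *The device effect must shrink and power be lost.* If 0.5 against 0.8 were dry-night rates at 6.2 a week, and each device cut wet nights by a fixed proportion, children at 2 a week would show 83.9% against 93.5%. The plan does not say which outcome 0.5 and 0.8 describe or what mix of frequencies will enrol, so this is a possibility and not a finding.

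**What to change.** - **3.4.3.1:** compare each child's dry-night proportion between arms with pretreatment wet nights per week as a covariate, and include the same covariate in a logistic model for cure. State this under 3.4.4 as well, which is now empty.
- **3.3.1, Visit 1:** record wet nights per week after urotherapy and before the envelope is opened, confirm the existing 5.3 criterion against that figure, and use it as the covariate.

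The analysis change is the main step; the re-count supports it by giving the covariate a fixed date. The cost is one extra question at a visit already scheduled, a few lines of analysis text and possibly a few more screen failures. Section 5.3.1 plans to screen 200 for 100 places, which leaves room for these.
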